#### **Potential risks:**

The risk to patients is minimal. Blood draws will be performed at a maximum of eight different time points during the course of their treatment and follow-up.

You may feel slight discomfort from the blood draws at the site of the needle stick. Slight swelling and bruising are fairly common but usually go away soon. Rarely, people may have a vasovagal syncope.

Vasovagal syncope (vay-zoh-VAY-gul SING-kuh-pee) occurs when you faint because your body overreacts to certain triggers, such as the sight of blood or extreme emotional distress. It may also be called neurocardiogenic syncope. The vasovagal syncope trigger causes your heart rate and blood pressure to drop suddenly. That leads to reduced blood flow to your brain, causing you to briefly lose consciousness.

Vasovagal syncope is usually harmless and requires no treatment. But it's possible you may injure yourself during a vasovagal syncope episode. Your doctor may recommend tests to rule out more serious causes of fainting, such as heart disorders.

All patients will be assigned a study number, and this number will be used in place of patient's names or identification numbers so there should be minimal risk of loss of patient confidentiality. The master sheet containing the patient number and study ID will be kept in a password protected database.

**PI: [name]**  
**IRB00047240**  
**NCT03167359**

**Version 04/01/2021**

We conducted a prospective study to assess the safety and feasibility of delivering 15 fractions of simultaneous integrated boost (SIB) radiotherapy for definitive breast cancer treatment.

**Data**

The SIB dataset was queried, and after exclusion and inclusion listed in the selection diagram file. Total 75 cases were included.

Selection and Exclusion Criteria	Sample Size	Excluded
SIB radiotherapy for breast cancer cases	75	-

**Outcome and definition**

1. Skin Thickening Ratio (STRA) Baseline
2. Skin Thickening Ratio (STRA) at 1 year
3. Change in Skin Thickening Ratio (STRA) from Baseline to 1 year
4. Overall Survival was defined as months from the date of radiation ended to death or last seen at Emory.
5. Local Recurrence-free Survival (LRFS) was defined as months from the date of radiation ended to local recurrence or last seen at Emory.
6. Distant Recurrence-free Survival (DRFS) was defined as months from the date of radiation ended to distant recurrence or last seen at Emory.

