#### **Primary Outcome Measure:**

- Cutaneous Toxicity Rate Cutaneous toxicity rate will be assessed by the National Cancer Institute Common Toxicity Criteria (NCI-CTC) v 3. grading scale.
- 1. Rate of 20% or greater increase in arm lymphedema (compared to baseline arm measurements) will be assessed Among breast cancer patients receiving regional nodal irradiation
- 2. Rate of Grade 3 brachial plexopathy will be assessed among breast cancer patients receiving regional nodal irradiation by RTOG and LENT/SOMA scales

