### Monitoring Plan for Severe Adverse Events:

We hypothesize that a maximum of 20% of patients might experience severe acute skin side effects defined as NCI-CTC Grade 3. This corresponds to symptoms interfering with activities of daily life. A Data Safety and Monitoring Board (DSMB) will monitor patient outcomes and suspend the protocol in the event that more than 16 of 80 patients demonstrate severe acute skin toxicity. During the study, the patients will be monitored continuously throughout the study such that if at any time during the study the upper limit of the number of patients developing Grade 3 toxicity exceed what is listed in the table below, the trial will be discontinued. With a 10% dropout rate, a total sample size of 83 patients was calculated to effectively test our hypothesis. For patients not requiring regional nodal irradiation, we will only collect adverse events related to skin toxicity, lung toxicity and heart toxicity. We will not report grade 1-2 radiation dermatitis as adverse events because most patients will at least have gr 1 dermatitis. We will keep a record of toxicity at each visit by collecting the Lent Soma evaluation of

the clinician at each visit after treatment starts. Patient reported fatigue rate will not be collected on the adverse event report, but will also be recorded at each visit

Total Patients	Upper limit of number of patients with toxicity for the trial to continue	Proportion of patients with toxicity if exceed the upper limit	Lower limit of 95% Cl	Upper Limit of 95% CI
3	<3	100%	29%	100%
4	<4	100%	40%	100%
5	<4	80%	28%	99%
6	<4	67%	22%	96%
7	<5	71%	29%	96%
8	<5	63%	24%	91%
9	<5	56%	21%	86%
10	<6	60%	26%	88%
11	<6	55%	23%	93%
12	<6	50%	21%	79%
13-50	<7	>20%	NA	

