# Patients Requiring Regional Nodal Irradiation

Among patients requiring regional nodal irradiation, we hypothesize that <3.0% of patients will develop severe brachial plexopathy following radiation to the regional nodes defined as LENT/SOMA or RTOG Grade 3 or higher (Continuous paresthesias with incomplete motor paresis; pain medication is generally required or objective neurologic findings with paresthesia or paresis) As this toxicity occurs after radiation treatment is complete, patients will be formally assessed for brachial plexopathy at baseline and at 7-12 weeks and 12-18 months post radiation for comparison with baseline assessments. However, patients will be asked to contact [name] if symptoms of brachial plexopathy develop in between or after study visits. We also hypothesize that less than 15% of patients receiving regional nodal irradiation will develop 20% or greater increase in arm lymphedema (compared to baseline measurements) assessed at 7-12 weeks and 12-18 months post radiation. Of note, lymphedema that develops in the context of weight gain (>/=15% increase in weight) or trauma to the arm will not be attributed to the radiation treatment itself and will not be considered an event to due to the treatment. If this side effect is secondary to radiation rather than surgery, it generally occurs after radiation is complete. Lymphedema that takes place during the 3 weeks of radiation or before radiation begins will be attributed to surgery. During the study, the patients

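### The SAP's outcome list and methods omit all three of the protocol's primary toxicity rates, so the SAP as written does not answer the safety question it restates

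*SAP*

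**What the plan says.** The protocol, under Primary Outcome Measure, names three rates:

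- Skin: "Cutaneous toxicity rate will be assessed by the National Cancer Institute Common Toxicity Criteria (NCI-CTC) v 3. grading scale".
- Lymphedema, in nodal patients: "Rate of 20% or greater increase in arm lymphedema (compared to baseline arm measurements) will be assessed".
- Plexopathy: "Rate of Grade 3 brachial plexopathy will be assessed among breast cancer patients receiving regional nodal irradiation by RTOG and LENT/SOMA scales".

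The monitoring sections attach expectations. For skin: "We hypothesize that a maximum of 20% of patients might experience severe acute skin side effects defined as NCI-CTC Grade 3". For plexopathy: "we hypothesize that <3.0% of patients will develop severe brachial plexopathy following radiation to the regional nodes". For lymphedema the figure is under 15%. In the nodal section the plexopathy event is "defined as LENT/SOMA or RTOG Grade 3 or higher". The protocol also says that "a total sample size of 83 patients was calculated to effectively test our hypothesis".

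The SAP opens by restating the aim of assessing safety and feasibility and reports 75 cases. Its Outcome and definition section lists skin thickening ratio at baseline, the same ratio at 1 year, "Change in Skin Thickening Ratio (STRA) from Baseline to 1 year", overall survival, local recurrence-free survival and distant recurrence-free survival. Its Study Cohort and Definition section gives a three-level toxicity scale worded around pain, analgesic use and activity. Its Statistical Analysis section names descriptive statistics for each variable, ANOVA, Pearson correlation and multiple linear regression.

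**The concern.** The trial's primary objective is safety and feasibility in patients at risk of skin toxicity, and the protocol turns it into three proportions with stated expectations. The SAP does not mention lymphedema, plexopathy, NCI-CTC grading, the three expected values or any confidence interval. Skin thickening is at most the first secondary outcome in the protocol, the ultrasound measure. An analyst who followed the SAP would deliver models of skin thickening and survival-type results, with no specified estimate for the question the trial was set up to answer.

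If toxicity counts were later added informally, with no interval, a small or zero count among about 30 nodal patients could be read as bearing out the under-3% expectation, which a cohort of that size cannot do.

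**Working it through.** **Step 1. Match outcomes.**

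| Protocol primary outcome | Expected value | In the SAP's six outcomes? | Method in the SAP that estimates it? |
|---|---|---|---|
| NCI-CTC v3 skin toxicity rate | at most 20% | No | None named |
| Arm lymphedema, 20% or greater increase (nodal) | under 15% | No | None named |
| Grade 3 brachial plexopathy (nodal) | under 3% | No | None named |

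Result: 0 of 3. ANOVA, Pearson correlation and linear regression describe associations. None of them gives a single-cohort proportion with its uncertainty.

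**Step 2. Is the gap filled elsewhere?** The protocol's stopping tables cover all three toxicities, but they are count limits for continuing accrual. Only the skin table carries 95% limits, and only up to 12 patients. Those limits are exact binomial (Clopper-Pearson): 6 of 12 gives 21.1% to 78.9% (table: 21% and 79%), and 3 of 3 gives 29.2% to 100% (table: 29% and 100%). Of the ten rows with limits, only the upper limit for 6 of 11 departs (table 93%, computed 83.3%). The protocol therefore already uses the interval method proposed here, but for monitoring and not for a final estimate.

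The protocol's total of 83 cannot be rederived as a test-based sample size, because no significance level, power or alternative is stated. This point does not depend on it.

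**Step 3. What would an interval show?** These figures describe precision only; the event counts are illustrative, since the documents give no results. For x events in n patients, the two-sided exact 95% limits are the 2.5% quantile of Beta(x, n−x+1) and the 97.5% quantile of Beta(x+1, n−x). With x = 0 the upper limit is 1 − 0.025^(1/n).

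Inputs: n = 75 from the SAP's Data section, assuming all are evaluable for skin toxicity; n = 30 from the protocol's nodal target under Data Collection.

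- Skin, n = 75: 8 events, 10.7% (4.7 to 19.9); 9 events, 12.0% (5.6 to 21.6); 22 events, 29.3% (19.4 to 41.0); 23 events, 30.7% (20.5 to 42.4). The interval contains 20% for every count from 9 to 22.
- Lymphedema, n = 30: 4 events, 13.3% (3.8 to 30.7). The estimate is below 15% but the interval extends well above it.
- Plexopathy, n = 30: 0 events, upper limit 1 − 0.025^(1/30) = 11.6%; 1 event, 3.3% (0.1 to 17.2).

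The SAP text gives no nodal cohort size, so a range is needed. With n = 25 (75 minus the breast-only target of 50, an assumption) the zero-event upper limit is 13.7%. With n = 33 (the planned nodal enrolment) it is 10.6%. Bringing it below 3% with zero events needs n > ln(0.025)/ln(0.97) = 121.1, that is, 122 patients.

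**The case against.** The best defence is that the protocol already does much of the work, and an SAP need not repeat protocol definitions for them to bind. Much of this stands.

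- A reader might infer that the trial has no event definition or denominator. It has most of both. The protocol names the nodal population and the 20% arm threshold, and its skin rule works from 80 patients. Only the handling of dropouts and non-evaluable patients is missing.
- A reader might infer that the analyst is free to count or ignore lymphedema that occurs with weight gain or arm trauma, or that begins before or during radiation. The protocol settles this: such cases are not attributed to radiation. Counting them would be a departure from the protocol.
- A reader might see a conflict between plexopathy graded by RTOG and LENT/SOMA (primary outcome) and by either scale (nodal monitoring section). The primary outcome most naturally lists the instruments, and Data Collection also uses the either-scale wording. What remains is whether Grade 3 includes higher grades.
- The SAP promises descriptive statistics for each variable and defines a toxicity scale, so a toxicity table may well exist. It cannot be claimed that toxicity went unreported. But the scale is tied to no outcome and is not identified as NCI-CTC, RTOG or LENT/SOMA, and no rate is specified.
- Neither document promises a final confidence interval, and the inability of about 30 patients to exclude 3% is a sample-size limit that no SAP wording can change. Both are fair. The interval is a recommendation and the 3% remark is a reporting caveat.

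None of this supplies an analysis of the three primary rates.

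**Conclusion.** The point holds as an omission: 0 of 3 primary outcomes appear among the SAP's six, and no named method estimates them. It is more than missing detail, because the SAP followed literally answers a different question from the one in its opening sentence. It should be corrected before the SAP is relied on as the analysis plan for the primary objective.

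The omission rests on the text alone and needs no numerical assumption. Only the precision figures do: that all 75 cases are evaluable for skin toxicity, and that the nodal cohort has about 30 patients (25 to 33 considered). The documents do not support saying that the endpoints are undefined, that toxicity was never tabulated, or that the hypothesised values are pass marks the trial must meet.

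**What to change.** Make the three protocol rates the primary analysis in the SAP, using definitions the protocol already gives:

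1. Skin: NCI-CTC v3, stating whether Grade 3 in the monitoring section includes higher grades.
2. Lymphedema: a 20% or greater increase from baseline in nodal patients, applying the protocol's attribution rules and reporting the number of events excluded under each.
3. Plexopathy: Grade 3 by either scale, as in Data Collection and the nodal monitoring section, stating whether Grade 3 in the primary outcome includes higher grades, as the nodal section does.

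For each rate, state how dropouts and non-evaluable patients enter the denominator. Show the estimate with an exact 95% interval beside the hypothesised 20%, under 15% or under 3%, and say that the interval is not a success criterion. Add the caveat that about 30 nodal patients cannot confirm a plexopathy rate under 3%. Label skin thickening ratio as the secondary ultrasound outcome, and say what the SAP's toxicity scale grades.

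The SAP is written in the past tense. If the analysis is already complete, add the rates as supplementary results and disclose that they were specified late.

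Cost: SAP wording and one or two tables from data the protocol already collects, with no new visits. Each lymphedema event needs a case check of weight, arm trauma and onset date. The intervals will be wide, and the under-3% expectation stays unconfirmed whatever is observed.

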### Background:

For the majority of women with breast cancer (BrCA), radiation therapy (XRT) is critical for preventing local recurrence and improving breast preservation and survival.[1] XRT to the whole breast is a necessary component of breast conserving therapy and is standard of care following partial mastectomy; XRT has been shown to decrease locoregional recurrence by 2/3 and improve absolute survival by a minimum of 5% over lumpectomy alone.[1]

As the number of survivors has markedly increased, clinicians are now seeking to reduce treatmentrelated toxicities and inconveniences of treatment, namely the traditional 6 weeks of daily radiotherapy. Skin thickening, fibrosis, and edema are some of the most common acute and potentially long-term debilitating toxicities of BrCA XRT.[2, 3] During XRT, approximately 50% of patients develop significant cutaneous toxicity including moist skin desquamation, erythema, and hyperpigmentation.[2, 3]

Two recent studies have examined the role of hypofractionation (>2Gy per day with shorter overall treatment time) in the treatment of breast cancer.[4, 5] A recently published Phase III Canadian study randomized early stage BrCA patients to 42.5 Gy in 16 fractions (fxns) (2.66 Gy per day) or 50 Gy in 25 fxns (2 Gy per day) to the whole breast following lumpectomy and axillary lymph node dissection. [4] At 10 years, there was no difference in local control, survival, or cutaneous toxicity.[4] The UK START B study also randomized patients to 40 Gy in 15 fxns (2.66 Gy per day) or 50 Gy in 25 fractions (2 Gy per day) and found no difference in local control, survival, or cosmesis at 5 years.[5] Both studies successfully challenged the long held radiobiological belief that large daily fractions (>2 Gy per day) portends severe late normal tissue toxicity and unacceptable breast cosmesis following XRT. More recently, an updated analysis of the UK START trial was presented with 9.8 years of follow-up and there was still no difference in local control, survival or side effects between hypfractionated radiation and standard five weeks of XRT treatment.[6]

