### **Preliminary Data:**

Recent work from our group indicates that ultrasound tissue characterization (UTC) may objectively and reliably measure XRT-induced cutaneous toxicity in BrCA patients. UTC is a non-invasive technique developed by [name], PH.D.(co-Investigator), to delineate sub-resolution tissue features that are not visible by standard B-mode ultrasonography.[22, 23] From the UTC analysis, we can obtain quantitative parameters (skin thickness, Pearson coefficient, and midband fit value) characterizing the dermal, hypodermal, and subcutaneous tissue. These spectral parameters are related to structural tissue properties including skin thickening, fibrosis, and edema. [22, 23] In published work, the clinical assessments of XRT-induced skin toxicity correlate strongly with UTC measurements and objectively validate this measurement of skin toxicity.[23] However, interobserver subjective toxicity assessments have mild to moderate agreement. UTC would provide a reproducible way of characterizing toxicity. XRT-induced skin thickening increases with maximum thickness occurring at the completion of XRT. The thickening decreases significantly by 6 weeks post XRT in patients treated with a traditional 6 week course of XRT. We plan to use UTC to objectively quantify cutaneous toxicity during XRT in this study. Time points for analysis of cutaneous toxicity (baseline, fraction 15 of XRT and 2 - 5 weeks, 7 - 12 weeks, and 12 - 18 months post XRT) are based on these data.[23].

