### Data Collection:

Cutaneous toxicity will be assessed at baseline, fraction 15 of XRT and 2 - 5 weeks, 7 - 12 weeks, and 12 – 18 months post XRT by objective ultrasound measurements (UTC). Photographs of the treated breast or chest wall as well as the contralateral breast will also be taken. Documentation of the UTC and photographs will be kept in electronic format for reference. For each visit after the baseline (after treatment has begun), cutaneous toxicity will be assessed by a clinician. Participants will be seen by the investigator in follow up at the third and/or fourth visits and at the fifth visit and an investigator dictation will be performed.

Patients who have had a mastectomy and plan for permanent breast reconstructive surgery after radiation will be assessed within one month of their permanent reconstructive surgery and 5 - 7 months following their surgery using the same procedures as described above. It is highly variable as to when reconstruction will occur. If these time points do not fall within the time frame for the regular study visits, additional study visits will be added for these patients.

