Information regarding disease characteristics (including stage, tumor size, grade), patient demographics (including age, race, co-morbidities, social history, body mass index), systemic treatment (including hormone therapy, systemic therapy), surgical treatment, radiation treatment, and clinical outcomes (local control, distant metastasis, survival, and treatment complications) will be collected and recorded.

Patients may also be asked to participate in a long term assessment between 1 and 10 years where they will complete the same study procedures as outlined above. Patients will be compensated \$50.00 for completing this visit.

A follow up phone survey will be taken between 18 months and 10 years after treatment. Using the same scales as in the study visits, the patients will be asked to rate their fatigue level, breast pain, how happy they are with the look of their breast and how different their radiated breast is from their non-radiated breast. They will also be asked if they are on any hormonal treatment for breast cancer and if so, the date they started. We will obtain verbal consent for this survey from patients who completed this study before the follow up phone survey was originally approved on 9/24/2013.

Assuming 10% of patients dropout, 53 patients requiring breast only radiation will be enrolled (2-3 patients per month) to yield a total of 50 patients.

An additional 33 patients requiring regional nodal irradiation and breast or chest wall radiation will be enrolled. Assuming 10% of patients dropout, 33 patients of these patients will be enrolled (2-3 patients per month) to yield a total of 30 patients receiving regional nodal irradiation and breast or chest wall radiation.

In patients undergoing regional nodal irradiation, arm measurements will be taken of the ipsilateral and contralateral upper extremity at baseline, 7 - 12 weeks, and 12 – 18 months post XRT by a licensed lymphedema therapist or study staff trained by a licensed lymphedema therapist. These patients will also be assessed for brachial plexopathy using RTOG grading toxicity, LENT/SOMA grading toxicity, and a modified version of a validated questionnaire to assess symptoms of brachial plexopathy at baseline and 7 - 12 weeks, and 12 – 18 months post XRT.[24] If a patient develops RTOG or LENT/SOMA Grade 3 toxicity, an objective measurement (MRI and/or nerve conduction studies) of brachial plexopathy will be employed.

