### Secondary Outcome Measures:

- 1. Rate of cutaneous toxicity, as measured by changes in cutaneous measurements, acquired vis ultrasound tissue characterizations (UTC)
- 2. Local control will also be assessed through routine physical examination, annual screening mammograms, ultrasound, and biopsy to confirm local recurrence.
- Blood will be analyzed for biomarkers and inflammatory markers including(tumor necrosis factor (TNF)-alpha, soluble TNF receptor 2 (sTNFR2), interleukin (IL)-6, IL-1ra, and C - reactive protein (CRP) as well as genetic factors to determine if they are associated with development of cutaneous toxicity.
- 4. Change in Multidimensional Fatigue Inventory (MFI) Score

[Time Frame: Baseline, End of Follow Up (Up to 18 months)] [Safety Issue: No]

The Multidimensional Fatigue Inventory (MFI) is a 20-item self-report instrument designed to measure fatigue. Scores range from 20 to 100. The higher the score, the more fatigued.

5. Change in Pittsburgh Sleep Quality Index (PSQI) Score

[Time Frame: Baseline, End of Follow Up (Up to 18 months)] [Safety Issue: No]

The PSQI is a self-rated questionnaire which assesses sleep quality and disturbances over a 1-month time interval. Scores range from 0 to 21. A score of less than or equal to 5 is associated with good sleep quality. A score greater than 5 is associated with poor sleep quality.

6. Change in Perceived Stress Scale (PSS) Score

[Time Frame: Baseline, End of Follow Up (Up to 18 months)] [Safety Issue: No]

The PSS is a self-reported instrument used to measure the perception of stress. Scores range from 0 to 40. Score of 20 or higher are considered high stress.

7. Change in Patient Reported Outcomes Measurement Information System (PROMIS) Fatigue Short Form Score

[Time Frame: Baseline, End of Follow Up (Up to 18 months)] [Safety Issue: No]

The PROMIS Fatigue questionnaire is a self-report tool used to evaluate frequency, duration, and intensity of fatigue over the past seven days. Scores range from 7 to 35. The higher the score, the more fatigue.

8. Change in an Inventory of Depressive Symptomatology-Self Reported (IDS-SR) score

[Time Frame: Baseline, End of Follow Up (Up to 18 months)] [Safety Issue: No]

The IDS-SR is a self-reported measure in which participants rate the frequency of depression symptoms within the past seven days. Scores range from 0 to 84, with higher score reflecting greater severity of depressive symptoms.

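### The SAP names skin-thickening outcomes only at baseline and 1 year, so if STRA is the ultrasound measure the expected peak has no named outcome; separately, regression predictors are screened in the same 75 cases

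*SAP*

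**What the plan says.** **Protocol.** Preliminary Data lists "Time points for analysis of cutaneous toxicity (baseline, fraction 15 of XRT and 2 - 5 weeks", followed by 7-12 weeks and 12-18 months after radiotherapy. Data Collection repeats the schedule and ties it to UTC: "Cutaneous toxicity will be assessed at baseline, fraction 15 of XRT and 2 - 5 weeks" and at the same two later visits. On the expected course, Preliminary Data states "XRT-induced skin thickening increases with maximum thickness occurring at the completion of XRT" and "The thickening decreases significantly by 6 weeks post XRT in patients treated with a traditional 6 week course of XRT". Background treats thickening as both an early and a late problem: "Skin thickening, fibrosis, and edema are some of the most common acute and potentially long-term debilitating toxicities". The Correlative Studies paragraph says the five UTC time points should help show how toxicity develops and resolves. Secondary outcome 1 is "Rate of cutaneous toxicity, as measured by changes in cutaneous measurements" by UTC, with no time point attached.

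**SAP.** Outcome and definition lists STRA at baseline, STRA at 1 year, "Change in Skin Thickening Ratio (STRA) from Baseline to 1 year", and three time-to-event outcomes. It does not define STRA, link it to UTC or give a window for 1 year. Statistical Analysis describes descriptive statistics for each variable, ANOVA, Pearson correlation and multiple linear regression, with no repeated-measures method. Regression variables are chosen by univariate significance, after allowing for collinearity and dropping variables with much missing data. The only data set named is the 75 cases in the Data section. The significance threshold and the number of candidate variables are not given.

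**The concern.** A baseline-to-1-year change gives the same answer for a patient whose skin never thickened and for one whose skin thickened sharply and then recovered. The trial assesses safety in women chosen because they were at raised risk of skin toxicity or under-represented in earlier trials. For them the early rise is part of the safety picture, and Preliminary Data promotes UTC because clinicians agree only mildly to moderately when grading toxicity. A patient without a 1-year scan also has no change score, however many earlier scans exist.

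The 1-year label is open as well. It could mean the 12-18 month visit, or the optional "long term assessment between 1 and 10 years where they will complete the same study procedures".

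The screening rule is a separate weakness. Background and Study Design name the risk factors in advance (prior chemotherapy, breast separation, race, age, nodal irradiation), yet the SAP lets the data choose the predictors and then tests them in the same data. The p-values that result cannot be taken at face value.

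**Working it through.** **1. Visit count.** The protocol has 1 baseline + 4 post-baseline visits = 5, which reproduces the five UTC time points stated under Correlative Studies.

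| Protocol UTC visit | Named SAP skin-thickening outcome (if STRA is UTC) |
|---|---|
| Baseline | Yes |
| Fraction 15 (last of 15 fractions; expected peak) | None |
| 2-5 weeks | None |
| 7-12 weeks | None |
| 12-18 months | Yes, if this is the 1-year visit |

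So 3 of 4 post-baseline visits have no named outcome. If 1 year means the optional long-term assessment, it is 4 of 4. If STRA is not a UTC measure, the SAP names no UTC outcome at all.

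**2. Clinician-graded toxicity.** The NCI-CTC skin toxicity rate is the protocol's primary outcome and is monitored by stopping tables. The SAP's outcome list omits it. The SAP does give a grade scale, but it is worded around pain and activity and is not listed as an outcome.

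**3. Precision if the missing visits are added.** The 95% CI half-width for a mean paired change, in SDs of change, is t(0.975, m−1)/√m:

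- m = 75 (SAP): 0.230
- m = 60 (assumed): 0.258
- m = 45 (assumed): 0.300

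**4. Screening with no real effects.** Assumed: n = 75, univariate p<0.05, then least squares on the variables selected; 10,000 simulations per setting. The table gives the chance that the final model holds at least one predictor with p<0.05.

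| Candidates k | 1 − 0.95^k | Independent | Correlation 0.3 |
|---|---|---|---|
| 5 | 22.6% | 22.6% | 18.9% |
| 10 | 40.1% | 39.2% | 29.4% |
| 20 | 64.2% | 61.4% | 39.6% |

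A screening threshold of 0.10 or 0.20 gives about 22%, 38% and 59% with independent candidates. These rates are close to, or below, plain multiplicity.

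**5. Screening with real effects.** Assumed: five real factors with slope 0.2 and residual SD 1, plus 5 or 15 null candidates.

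- A false predictor appears in 15% or 38% of analyses.
- Each real factor is selected about 35% of the time, and its estimate is then about 1.5 times too large.
- If total outcome variance is fixed at 1 instead, the figures are about 41% and 1.4 times.
- CI coverage for the selected real factors stays near 94-95%.

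**6. Missing 1-year scans.** The documents give no rate or mechanism. Assumed: about 26% missing, n = 75, visit correlation 0.3 or 0.5. Bias in mean 1-year change, in baseline SDs:

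| Missingness depends on | Paired completers | Five-visit mixed model (likelihood estimate) |
|---|---|---|
| Observed fraction-15 change | −0.13 / −0.11 | about 0 / 0 |
| Unobserved 1-year change | −0.26 / −0.22 | −0.16 / −0.14 |

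In the first row, 95% CI coverage is about 88% for completers and 94% for the mixed model. The model removes the bias only when missingness depends on observed values.

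**7. Degrees of freedom for a fixed-factor regression.** Intercept + baseline STRA + five factors = 7 parameters. All 75 scanned: 75 − 7 = 68. With 25% of 1-year scans missing (assumed): 0.75 × 75 ≈ 56, and 56 − 7 = 49.

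**The case against.** The strongest reply is that no explicit commitment is broken. Secondary outcome 1 sets no time point, so a 1-year change is a permissible form of it. The list of analysis times sits in Preliminary Data, Data Collection is only a schedule, and the Correlative Studies wording is tentative. The SAP's descriptive statistics may already cover the other visits. All of this stands. A reader might infer that the early scans went unanalysed or that the SAP contradicts its secondary outcome; the documents show neither. What remains is that nothing commits the team to reporting the visits the protocol set for analysis.

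A reader might also assume that clinician grading fills the gap. The protocol does define and monitor it, so it was not neglected, but the SAP does not list it as an outcome.

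On screening, the SAP makes no confirmatory claim, and most of the false-positive rate is ordinary multiplicity. Both are fair. A reader might infer that screening invalidates every interval in the model; where a real factor is selected, coverage holds near its nominal level under the slopes assumed here. The remaining harms are false predictors and inflated estimates.

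Finally, a mixed model should not be presented as a cure for missing scans, as step 6 shows.

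**Conclusion.** The point holds in two parts. First, the SAP leaves STRA and 1 year undefined. If STRA is the UTC measure, 3 of 4 post-baseline visits, including the expected peak, have no named outcome. The peak is itself an expectation, and the fall by 6 weeks was seen after a traditional 6-week course. Late change is a legitimate outcome and should stay. The clinician-graded skin toxicity rate is also absent from the SAP's outcome list.

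Second, p-values for predictors screened in the same 75 cases are not valid at face value. The size depends on assumptions about threshold, number of candidates, their correlation and effect size, none of which the documents give: roughly 19% to 61% of all-null analyses over 5 to 20 candidates, and an overestimate of about 1.4 to 1.5 times for real effects that pass. The visit count and the screening flaw do not depend on these figures.

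The UTC change is a secondary measure in a safety and feasibility study, so this is a correction worth making and does not undermine the trial.

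**What to change.** 1. Define STRA (numerator, denominator, whether it comes from UTC) and state which visit and window count as 1 year.
2. Keep the 1-year change. Add paired change from baseline at fraction 15, 2-5 weeks and 7-12 weeks, each with the number of paired scans, mean and 95% CI.
3. Optionally add, as a sensitivity analysis, a mixed model with all five STRA values as responses, and state the missingness assumption it relies on.
4. Replace univariate screening with two regressions, STRA at fraction 15 and at 1 year, each on baseline STRA, prior chemotherapy, separation above 25 cm, race, regional nodal irradiation and age. State the number of patients actually analysed in each.
5. List the clinician-graded skin toxicity rate among the SAP outcomes.
6. Label any screened predictors exploratory, and any analysis added after results were seen post hoc.

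**Cost.** The SAP is dated 04/01/2021 and written in the past tense, so this means an addendum and a labelled post hoc analysis. No new visits are needed, and the protocol says UTC records are kept electronically. Expect more programming, possible extraction of stored scans, incomplete data at the middle visits, and fewer predictors reported as significant.
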